9.2.2 Dosing and Administration

All patients will self-administer entinostat/placebo PO once weekly on study days 1, 8 and 15 of each 21 day cycle. A new bottle of entinostat/placebo will be dispensed on day 1 of each cycle, regardless of the number of pills remaining in the bottle from the previous cycle.

On study days on which patients receive both entinostat/placebo and atezolizumab, entinostat/placebo is to be taken prior to atezolizumab.

Entinostat/placebo is to be taken on an empty stomach, at least 2 hours after a meal and at least 1 hour before the next meal.

If an entinostat/placebo dose is missed, it may be taken up to 48 hours after the scheduled dosing time. If it is not taken within the 48 hour window, the dose should not be taken and will be counted as a missed dose. The patient should take the next scheduled dose per protocol. Missed doses should be noted as such on the patient drug diary and in the eCRF.

If entinostat/placebo is vomited, dosing should not be re-administered but instead the dose should be skipped.

9.2.2.1 Phase 1b

During the Phase 1b Dose Determination Phase, all patients will receive atezolizumab 1200 mg IV on D1 of each 21 day cycle. They will also receive entinostat orally weekly on days 1, 8 and 15 of each cycle at either 5 mg, 3 mg or 2 mg. Both drugs will be given in an open-label fashion.

Patients who discontinue from the study treatment for reasons other than study drug-related toxicity before completing C1 may be replaced (refer to [section 9.4](#)).

9.2.2.2 Phase 2

During the Phase 2 Dose Expansion Phase, all patients will receive atezolizumab 1200 mg IV on D1 of each 21 day cycle. They will also receive the RP2D of entinostat or matched placebo weekly on days 1, 8 and 15 of each cycle. Entinostat/placebo will be given in double blind fashion.

Any detected cumulative toxicity may require later dose reductions and/or other changes to the dosing schedule, as appropriate, including further refinement of the RP2D.

9.3 Atezolizumab

9.3.1 Supply and Storage

Atezolizumab is a humanized monoclonal antibody that blocks the interaction between PD-1 and its ligands, PD-L1 and PD-L2. Atezolizumab is an IgG4 kappa immunoglobulin with an approximate molecular weight of 149 kDa.

Atezolizumab drug product is provided in a single-use, 20-mL USP/PH. Eur. Type 1 glass vial as a colorless-to-slightly-yellow, sterile, preservative-free clear liquid solution intended for IV administration. The vial is designed to deliver 20 mL (1200 mg) of atezolizumab solution but may contain more than the stated volume to enable delivery of the entire 20-mL volume. The atezolizumab drug product is formulated as 60 mg/mL of atezolizumab in 20 mM histidine acetate, 120 mM sucrose, 0.04% polysorbate 20, pH 5.8.

Atezolizumab must be refrigerated at 2°C–8°C (36°F–46°F) upon receipt until use.

Atezolizumab vials should not be used beyond the expiration date provided by the manufacturer. No preservative is used in the atezolizumab drug product; therefore, each vial is intended for single use only. Vial contents should not be frozen or shaken and should be protected from direct sunlight.

Atezolizumab is supplied by Syndax to the sites and is given intravenously.

9.3.2 Dosing and Administration

The dose level of atezolizumab in this study is 1200 mg administered by IV infusion q3w.

Administration of atezolizumab will be performed in a setting with emergency medical facilities and staff who are trained to monitor for and respond to medical emergencies.

The initial dose of atezolizumab will be delivered over 60 (± 15) minutes. If the first infusion is tolerated without infusion-associated adverse events, the second infusion may be delivered over 30 (± 10) minutes. If the 30-minute infusion is well tolerated, all subsequent infusions may be delivered over 30 (± 10) minutes, otherwise it should be delivered over 60 (± 15) minutes. The patient's vital signs (heart rate, respiratory rate, blood pressure, and temperature) should be determined no more than 60 minutes before each atezolizumab infusion. Vital signs should also be obtained during or after the atezolizumab infusion if clinically indicated.

No premedication will be allowed for the first dose of atezolizumab. Premedication may be administered for subsequent infusions at the discretion of the treating physician after consultation with the Medical Monitor.

Any overdose or incorrect administration of study drug should be noted on the Study Drug Administration electronic eCRF. Adverse events associated with an overdose or incorrect administration of study drug should be recorded on the Adverse Event eCRF.

Refer to the Pharmacy Manual for complete details regarding supply, storage, accountability, and destruction of Atezolizumab.

9.4 Study Drug(s) Accountability

The lot number(s) of the study drugs (entinostat and atezolizumab) received at the site are to be recorded on the Drug Accountability Log maintained by the pharmacist. Additional distribution and return information will also be recorded at the site.

Patient medication instructions and dosing diaries will be provided to the patient for purposes of recording entinostat/placebo self-administration.

9.5 Entinostat Compliance

Treatment compliance to entinostat will be assessed at the end of each cycle. Patients will complete a diary to document their weekly intakes. They will be instructed to return all unused drugs (partially used and empty containers) and their diary at each visit. Site staff will perform accountability of the returned drug and will assess patient compliance. Site staff must ensure that the patient clearly understands the directions for self-medication and follows the schedule.

9.6 Dose-limiting Toxicity

In the Dose-Determination Phase, DLTs will be assessed during the DLT assessment window, which is defined as the first cycle of treatment. The DLT assessment window (Cycle 1) is the time period between C1D1 until C2D1 (expected to be 21 days after C1D1).

In addition, the total dose of entinostat received over the first two cycles has to be evaluated as it corresponds to one of the DLT criteria.

A patient will be considered DLT evaluable if she:

- Incurs an adverse event meeting DLT criteria during Cycle 1

Or

- Completes Cycle 1 and receives the full dose of atezolizumab and all doses of entinostat during this cycle, without incurring a DLT. In case a patient would not begin Cycle 2 for reasons other than a DLT, she would be considered DLT evaluable if she receives all planned doses of entinostat and atezolizumab during cycle 1 and completes 7 days after C1D15 without incurring a DLT.

Patients who are not considered DLT evaluable may be replaced to complete a cohort.

DLT is defined as the occurrence of any of the following events within **the DLT Assessment window** that are considered by the Investigator to be at least possibly related to study drug:

- Grade 5 events
- Grade ≥ 4 neutropenia ($ANC < 500/\mu L$) lasting ≥ 7 days
- Grade ≥ 3 febrile neutropenia
- Grade ≥ 4 thrombocytopenia lasting > 48 hours
- Grade ≥ 4 anemia
- Grade ≥ 4 rash (cont'd on next page)
- Grade ≥ 3 symptomatic hepatic toxicities that do not resolve to Grade ≤ 2 within 48 hours or Grade ≥ 3 asymptomatic hepatic toxicities that do not resolve to Grade ≤ 1 within 3 weeks of onset with the following **exception**:
 - For patients with Grade 2 AST, ALT, and/or alkaline phosphatase abnormality at enrollment, an increase to $> 10 \times$ the upper limit of normal (ULN) that does not resolve to Grade ≤ 2 within 48 hours (if symptomatic) or that does not resolve to Grade ≤ 1 within 3 weeks of onset (if asymptomatic) will be considered a DLT.
- Grade ≥ 3 non-hematologic, non-hepatic organ toxicity, with the following **exceptions**:

- Grade 3 immune-related adverse event that resolves to Grade ≤ 1 within 3 weeks of its onset
- Grade 3 nausea or vomiting that resolves to Grade ≤ 1 within 72 hours of appropriate supportive therapy
- Grade ≥ 3 fatigue that resolves to Grade ≤ 2 within 7 days
- Grade 3 arthralgia that can be adequately managed with supportive care or that resolves to Grade ≤ 2 within 7 days
- Grade 3 fever (in the absence of any clinically significant source of fever) that resolves to Grade ≤ 2 within 7 days with supportive care
- Grade ≥ 3 laboratory abnormality that is asymptomatic and deemed by the investigator not to be clinically significant
- Grade 3 autoimmune thyroiditis or other endocrine abnormality that can be managed by endocrine therapy or hormonal replacement
- Grade 3 tumor flare defined as local pain, irritation, or rash localized at sites of known or suspected tumor
- Grade 3 infusion reaction that resolves within 6 hours to Grade ≤ 1
- Inability to receive all 3 doses of entinostat during the first cycle

In addition, the inability to receive greater than 60% of the planned entinostat dose during the first 2 cycles, will also be considered a DLT.

All DLTs will be reported on the AE eCRF in the EDC system within 24 hours. All DLTs will be considered adverse events of special interest for this protocol and will be reported to TRIO in an expedited manner. Please see Protocol [Section 12.4](#) and also refer to the Adverse Event Reporting Procedures in the Study Manual.

Patients who experience a DLT will be allowed to remain on study if they meet the following criteria: (1) the investigator believes it is appropriate for patients to remain on study (2) the event has resolved and no longer meets the definition of DLT and (3) the timeline for resolution falls within the guidelines for dose delays ([Section 9.10](#)).

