9.10 Dose Interruptions and Modifications

Although entinostat and atezolizumab have distinct toxicity profiles, they do share some AEs such as fatigue and nausea. There is also the possibility that 1 agent may potentiate the other and hence drug causality will not always be clear. In the event of uncertainty, dose reductions or delays will follow the most conservative approach (i.e., delays and/or dose reductions for both drugs) until resolution of the event, or the patient is taken off study. However, if the toxicity is clearly associated with only one of the study drugs, then the other study drug may be continued at the discretion of the study investigator in consultation with the Medical Monitor, until resolution of the event or the patient is taken off study.

Note: If a patient permanently discontinues either study drug (entinostat/placebo or atezolizumab), the patient will be taken off study treatment

No dose reductions will be performed for atezolizumab.

Guidance for entinostat delays and or dose reductions can be found in Protocol [Section 9.10.1](#) . All dose modifications should be based on the AE requiring the greatest modification and should be properly documented in source documents. Investigators may take a more conservative approach than the guidelines outlined in the protocol on the basis of clinical judgment that is in the best interest of the subject. Such instances should be reported to the Medical Monitor.

Expected AEs for each agent are summarized in [Section 12](#).

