3.1 Phase 1b Dose Determination Phase

This study phase employs a classical 3+3 design, with the determination of DLT and the MTD or RP2D at cycle 1 based on the combination of entinostat (at the dose of 5mg, 3mg or 2mg weekly) with atezolizumab at a fixed dose of 1200 mg iv. Six patients will need to be treated in a dose level for it to be considered MTD or the RP2D. The recommended dose for Phase 2 investigation will be the higher of either 2, 3, or 5mg weekly PO that results in less than a 33% incidence of DLT.

Note: Based on evaluation of the safety and tolerability data gathered during the dose determination phase together with data from other clinical trials, it may also be decided that accrual will take place at an alternate dose level or dosing schedule via a protocol amendment.

Up to 18 patients are expected to be enrolled in the Dose Determination Phase of the study.

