6.7 Dose-limiting Toxicity (DLT)

DLT is defined as the occurrence of specific events defined in Section 9.6 of the protocol within the first cycle of treatment (i.e. between Day 1 to Day 21 of Cycle 1) of entinostat in combination with atezolizumab that are considered by the investigator to be at least possibly related to study drug using the National Cancer Institute (NCI) Common Terminology Criteria for Adverse Events (CTCAE) version 4.03.

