Title	Population	Description
		and the corresponding DLT at cycle 1 and 2 for each treatment group. For Phase 1b only.
Progression-Free Survival	FAS ¹	Summary of PFS results including treatment comparison results. Separate tables will be done for PFS based on RECIST 1.1 and irRECIST.
Progression-Free Survival	FAS ¹	Summary of PFS results including treatment comparison results (sensitivity analysis). Separate tables will be done for PFS based on RECIST 1.1 and irRECIST.
Objective Response Rate	FAS ¹	Summary of ORR results including treatment comparison results. Separate tables will be done for ORR based on RECIST 1.1 and irRECIST.
Clinical Benefit Rate	FAS ¹	Summary of CBR results including treatment comparison results. Separate tables will be done for CBR done based on RECIST 1.1 and irRECIST.
Overall Survival	FAS ¹	Summary of OS results by treatment group.
Duration of Response (those with CR/PR or irCR/irPR)	FAS ¹	Summary of DOR results by treatment group.
Time to Response (same comment as above)	FAS ¹	Summary of TTR results by treatment group.
TEAEs Overview	Safety	Tabulates the number of patients with TEAEs, Related TEAEs, Grade 3 / 4 TEAEs, TEAEs with action taken as dose reduced or drug interrupted, TEAEs leading to drug withdrawn, SAE, Fatal AE. For Phase 1b, the DLT rate will be presented.

**Statistical Analysis Plan
SNDX-275-0602 (TRIO025)
DM-025-037**

Title	Population	Description
TEAEs	Safety	Summary by SOC and PT for each treatment group.
TEAEs	Safety	Summary by PT for each treatment group ordered by frequency.
TEAEs per Maximum Grade	Safety	Summary by SOC and PT for each treatment group.
TEAEs Related to Entinostat	Safety	Summary by SOC and PT for each treatment group.
TEAEs Related to Entinostat per Maximum Grade	Safety	Summary by SOC and PT for each treatment group.
Grade 3 / 4 TEAEs	Safety	Summary by SOC and PT for each treatment group.
Grade 3 / 4 TEAEs	Safety	Summary by PT for each treatment group ordered by frequency.
TEAEs Related to Atezolizumab	Safety	Summary by SOC and PT for each treatment group.
TEAEs Related to Atezolizumab per Maximum Grade	Safety	Summary by SOC and PT for each treatment group.
TEAEs Related to Entinostat and/or Atezolizumab	Safety	Summary by SOC and PT for each treatment group.
TEAEs Related to Entinostat and/or Atezolizumab per Maximum Grade	Safety	Summary by SOC and PT for each treatment group.

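### SAP 6.7 confines DLTs to Cycle 1 and so drops the protocol's two-cycle entinostat dose criterion, which can understate the reported Phase 1b DLT rate

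*Protocol*

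**What the plan says.** **Protocol 9.6** sets the window first: "The DLT assessment window (Cycle 1) is the time period between C1D1 until C2D1 (expected to be 21 days after C1D1"). It then adds that "the total dose of entinostat received over the first two cycles has to be evaluated as it corresponds to one of the DLT criteria". A list of toxicities follows; these count if the investigator judges them at least possibly related to study drug. After the list, in a paragraph of its own and without that condition, comes the two-cycle rule: "the inability to receive greater than 60% of the planned entinostat dose during the first 2 cycles, will also be considered a DLT".

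The same section deals with a patient who stops early: "In case a patient would not begin Cycle 2 for reasons other than a DLT, she would be considered DLT evaluable", provided that she had all planned Cycle 1 doses and went 7 days past C1D15 without a DLT.

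**SAP 6.7** refers to the events in protocol 9.6 but places them "within the first cycle of treatment (i.e. between Day 1 to Day 21 of Cycle 1"). It applies the relatedness condition to all of them. **SAP 3.1** describes a 3+3 design "with the determination of DLT and the MTD or RP2D at cycle 1"; protocol 6.1 and the synopsis likewise base the determination on C1.

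**SAP 11.1** plans a table of patients with a DLT "and the corresponding DLT at cycle 1 and 2 for each treatment group. For Phase 1b only". SAP 10.9.2 reports the DLT rate per cohort as a crude proportion with an exact 95% confidence interval.

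**The concern.** The two-cycle criterion is deliberate: protocol 9.6 states it twice, once as something that must be evaluated and once as a rule. The SAP definition removes it, because shortfall in Cycle 2 dosing cannot be an event of Cycle 1 Days 1 to 21. The cross-reference to protocol 9.6 does not restore it, since the time limit is applied to whatever 9.6 contains. The SAP also disagrees with itself: a programmer cannot apply 6.7 strictly and still fill a table of Cycle 2 DLTs.

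DLT, MTD or RP2D is the Phase 1b primary endpoint (SAP 4.1). The patients lost are those who get through Cycle 1 and then cannot be given entinostat, which is the problem that the criterion was written to catch.

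A smaller matter sits beside it. The protocol's 60% sentence carries no relatedness condition, while the SAP requires relatedness for every DLT. The two documents could therefore classify differently a patient who misses doses for a reason other than toxicity.

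**Working it through.** **The plan's own figures.** Protocol 13.1.1 and SAP 5.2.1 give a 3% chance of halting at a true DLT rate of 5% and 83% at 50%. Under the 3+3 rule:

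P(halt) = P(≥2 of 3) + P(exactly 1 of 3) × P(≥1 of the next 3).

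- p = 0.05: 0.00725 + 0.13538 × 0.14263 = 0.0266 (stated 3%).
- p = 0.50: 0.500 + 0.375 × 0.875 = 0.828 (stated 83%).

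Both reproduce. They take the DLT rate as given, so they neither depend on nor settle what counts as a DLT.

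**Who meets the two-cycle criterion.** Entinostat is taken on Days 1, 8 and 15 (protocol 9.2.2): 3 doses per cycle, 6 over two cycles. Fraction received = mg taken in Cycles 1 and 2 ÷ (6 × assigned dose). A DLT requires a fraction not greater than 60%. With a full Cycle 1:

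| Assigned dose | Cycle 2 doses taken | Fraction | Protocol 9.6 |
|---|---|---|---|
| any | none | 3/6 = 50.0% | DLT |
| 5 mg | one at 3 mg | (15+3)/30 = 60.0% | DLT |
| 5 mg | one at 5 mg | (15+5)/30 = 66.7% | not a DLT |
| 5 mg | two at 3 mg | (15+6)/30 = 70.0% | not a DLT |
| 3 mg | one at 2 mg | (9+2)/18 = 61.1% | not a DLT |

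**Whether the protocol allows such a patient.** Suppose that Cycle 1 is fully dosed and a Grade 2 event clearly due to entinostat leads to holds on C2D1, C2D8 and C2D15.

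- A Grade 2 event is not on the DLT list. Table 9-1 lets the investigator interrupt dosing for it, in consultation with the Medical Monitor.
- Atezolizumab can go on, because "if the toxicity is clearly associated with only one of the study drugs, then the other study drug may be continued" (protocol 9.10).
- The footnote to Table 9-1 ends study drug only if more than half the doses in six weeks are missed. Here 3 of 6 is exactly half.

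She received 50%, so she is a DLT under protocol 9.6. With no listed Cycle 1 event, she is not a DLT under SAP 6.7.

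**Effect on the reported result.** Take six patients, one of them as above and one other with a listed Cycle 1 DLT. Exact (Clopper–Pearson) 95% limits:

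- Counted under protocol 9.6: 2/6 = 33.3% (4.3% to 77.7%).
- Counted under SAP 6.7: 1/6 = 16.7% (0.4% to 64.1%).

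The MTD definition in both documents asks for fewer than 33% of 6. The first count does not meet it and the second does, so the reported rate could disagree with the decision taken during the trial.

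**Relatedness.** A fully dosed patient who progresses or withdraws before Cycle 2 also has 3/6 = 50%. Read alone, the 60% sentence makes her a DLT. The evaluability clause treats her as evaluable without one.

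**The case against.** The strongest reply is that SAP 6.7 does not drive dosing. Sites report DLTs within 24 hours under protocol 9.6, the sponsor's study physician approves the start of the Phase 2 expansion, and the RP2D is set in discussion with the Medical Monitor and investigators (protocol 9.8). The SAP analysis is run only at completion of the dose determination phase (SAP 5.4.1). This stands. A reader might infer that the mismatch could select the wrong dose, and might attach a probability to that; the documents show no route from SAP 6.7 to a cohort decision.

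Second, SAP 6.7 points to protocol 9.6 and the planned table covers both cycles, so a careful programmer may count correctly anyway. That lowers the risk but leaves two conflicting instructions in one SAP.

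Three further inferences go too far:

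- *That Day 21 shortens the window.* The protocol expects C2D1 21 days after C1D1, so on schedule Days 1 to 21 are the period up to C2D1. The texts differ only if C2D1 is late.
- *That no cohort should clear until the two-cycle dose is known.* The synopsis clears cohorts after assessments through C2D1. That is a debatable choice, not an error: dosing starts at the highest level and only steps down, later-cycle safety is reviewed continuously, and the RP2D can be refined.
- *That the 60% sentence plainly counts progression as a DLT.* The word inability, the section's subject and the evaluability clause all point to toxicity. What remains is an ambiguity worth a phrase.

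**Conclusion.** The concern holds as a definition mismatch of minor to moderate weight. SAP 6.7 omits a DLT criterion that protocol 9.6 sets out deliberately, and it contradicts the DLT table in SAP 11.1. The consequence is a possible undercount in the reported DLT rate and its exact interval; one patient in six moves the estimate by 16.7 percentage points.

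This rests on SAP 6.7 being applied as written, and on a patient who completes Cycle 1 and then receives 60% or less over two cycles because of related toxicity. The documents do not say how often that would happen, and no frequency is assumed. The missing relatedness condition in the protocol is a separate, smaller ambiguity that could work the other way, by adding patients who stopped for progression or withdrawal.

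**What to change.** 1. In SAP 6.7, define DLT as Cycle 1 events per protocol 9.6 (C1D1 until C2D1), plus the two-cycle 60% entinostat dose criterion. Tying the window to C2D1 also covers a late visit. The table in SAP 11.1 then needs no change.
2. Bring the phrases that place DLT determination in Cycle 1 into line in SAP 3.1, protocol 6.1 and the synopsis. Changing the SAP alone would leave the same wording in the protocol.
3. In protocol 9.6, limit the 60% sentence to doses missed for reasons at least possibly related to study drug. A fully dosed patient who stops before Cycle 2 for progression or withdrawal is then not counted, in agreement with the evaluability clause.

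The cost is a few sentences: no extra patients, visits or procedures, and no added wait before a cohort is cleared. Items 2 and 3 touch the protocol and so need the amendment approvals in protocol 15.1. Item 1 can be made in the SAP alone and removes the main mismatch.

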9.7 Maximum Tolerated Dose

MTD is defined as the highest dose level at which <33% of 6 patients experience DLT.

9.8 Recommended Phase 2 Dose

The RP2D will be equal to or less than the preliminary MTD. The RP2D will be determined in discussion with the Sponsor, Medical Monitor, and Dose Determination Phase Investigators. Additionally, observations related to immune correlates, and any cumulative toxicity observed after multiple cycles may be included in the rationale supporting the RP2D.

9.9 Treatment Duration

The duration of treatment for this study is expected to be 1 year. Patients may remain on study until unequivocal progressive disease, unacceptable toxicity, or another treatment withdrawal criteria is met per Protocol [Section 11](#). Study patients with evidence of radiological progressive disease who meet the criteria set forth in Protocol [Section 10.3.2](#) for “Treatment After Initial Radiological Progression”, should continue treatment and be followed according to irRECIST as described in [section 10.3.2](#). Any questions should be directed to the Medical Monitor.

If a patient permanently discontinues either study drug (entinostat/placebo or atezolizumab), the patient will be taken off study treatment and followed for progressive disease per protocol guidelines, or overall survival should progressive disease have been previously determined on study. Patients will receive standard of care outside the auspices of this study at the Investigator's discretion.

After discontinuation of study treatment, patients will complete an EOT visit within 7 days (+/- 3 days) after the last study drug dose and a Safety F/U visit 30 days (+/- 3 days) thereafter.

After completion of the 30-day Safety F/U visit, patients who have not experienced PD are to continue to undergo radiological assessments every 6 weeks until study week 36, and then every 9 weeks thereafter until progressive disease. The purpose of the post-treatment follow-up is to ascertain the duration of PFS for all patients in the study.

After they experience PD, surviving patients are to be contacted every 3-months for documentation of subsequent therapies and survival until closure of the study or patient death, whichever should occur first.

